DURATION OF THE STUDY: The total duration of study participation for each patient will be a maximum of 6 months consisting of: screening and baseline assessments; detoxification (13 days); and, follow-up evaluations conducted at 1, 3, and 6 months after enrollment. It is estimated that 2 patients will be enrolled per site per week with a total of 6 sites. Thus, the estimated length of enrollment is 30 weeks.

SAFETY ASSESSMENTS: Before any study procedures are performed, patients will be required to provide signed informed consent. All candidates for study enrollment will have a physical examination including vital signs and weight, medical history and history of prior medication use assessment, and psychiatric evaluation (ASI Lite) including a DSM-IV checklist for substance dependence, HIV risk assessment, and clinical laboratory studies (blood chemistry, hematology, Hepatitis B and C serology, and urinalysis) performed during screening/ baseline. All patients will have a 12-lead electrocardiograph (ECG). Females will be given a pregnancy test. Assessments of adverse events (AEs) and concomitant medication use will be performed daily during detoxification and at the one-month visit. Serious Adverse Events (SAEs) will be reported during the treatment and follow-up phases of the study.

OUTCOME ASSESSMENTS: Abstinence from opiates, amphetamines, cocaine, cannabinoids, methadone, and benzodiazepines will be assessed by urine drug screen measured at baseline, throughout detoxification, and at follow-up. Treatment retention will be calculated as the number of days each patient received his/her detoxification medication. The patient's status in the study will be tracked with a Study discharge report (SDR). The dispensing of ancillary medications will be tallied and grouped according to symptomology (several medications are permitted for treating anxiety, insomnia, nausea, etc.) and day during detoxification. Withdrawal symptoms will be assessed using the clinical opiate withdrawal scale (COWS), the adjective rating scale for withdrawal (ARSW), and visual analog scales (VAS) during detoxification and at follow-up (COWS and ARSW only). Additional measures of overall treatment effect will include a

shortened version of the Addiction Severity Index (ASI Lite), a client satisfaction questionnaire (CSQ), and SF-36 Health-related Quality of Life questionnaire administered at baseline and all follow-ups.

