5.0 STUDY OBJECTIVES

The primary objective of this clinical investigation is:

To compare the relative clinical utility of BUP/NX to clonidine in a short-term (13-day) opiate detoxification initiated in an inpatient setting. It is hypothesized that BUP/NX detoxification, compared to clonidine, will be associated with a better treatment response. A treatment responder is anyone who completes the 13-day detoxification and whose last urine specimen collected on day 13 or 14 is negative for opiates.

Other primary objectives are:

To determine the effect of treatment on:

- 1) abstinence from opiate and other drugs of abuse throughout the detoxification period and during longer term follow-up,
- 2) withdrawal symptoms,
- 3) treatment retention,
- 4) safety,
- 5) patient satisfaction with the treatment, and
- 6) extent of ancillary medications dispensed.

Analysis of the data designed to assess the other primary objectives in combination with the primary objective will provide a comprehensive overview of the relative clinical utility (effectiveness) of the two treatment regimens.

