11.5.2 Clonidine

Patients receiving oral clonidine will be instructed to swallow all pills and/or to leave their clonidine patch in place until replaced by medical personnel or until medical personnel directs the patient to change their dosage. The clonidine detoxification protocol was designed to reflect what is being used in clinical practice at a number of the participating CTP sites. Patients will be seen daily, on days of outpatient clinic operations.

In outpatient CTP sites, clonidine detoxification should be started early in the week (Tuesday or Wednesday [see section 11.4]) to insure a steady state level before the weekend with less medical staff. Medical personnel familiar with clonidine need to be available during clonidine treatment for daily patient monitoring, dose adjustment, and prescribing ancillary medication. Medical personnel should be familiar with monitoring vital signs for orthostatic changes and responding to any changes noted. Insure consistency in monitoring by using the same B.P. device at each visit.

Clonidine Dosing Procedure:

Day 1:

Encourage patients to drink lots of fluid. Dehydration exaggerates the hypotensive effects of clonidine. Before administering the test dose of clonidine, ask patients for any history of hypertension or hypotension, fainting or dizziness on rising. Take vital signs noting especially the systolic B.P. Check the EKG to insure the PR interval is not prolonged i.e. > .20 seconds. If the patient has systolic B.P. < 100 mm Hg or heart rate < 56 bpm, do not proceed with the clonidine test dose. Reassess patient if clinically warranted or discontinue the patient from the study.

Be cautious with patients with a history of hypertension or hypotension, fainting or dizziness on rising. Instruct all patients to get up slowly while taking clonidine (e.g. "sit up, swing your feet, and count to 10 before getting up").

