The clonidine patch is a 0.2 mm square that is applied in the same manner as a self-adhesive bandage. It is available in three sizes: 3.5, 7.0, and 10.5 cm². In a 24-hour period, these patches deliver an amount of clonidine equivalent to twice-daily dosing with 0.1, 0.2 or 0.3 mg of oral clonidine, respectively. Once the patch is placed on the epidermal surface, clonidine enters the circulatory system through the skin. A rate-limiting membrane within the patch governs the maximum amount absorbed. The patch supplies clonidine for up to 7 days. Only one strength will be used (0.1). Multiple patches can be placed on the patient's upper body, and removed if clinically indicated. (TIP series, number 19 reference).

Day 2:

It takes 2 days for the clonidine patches to achieve a maximum blood concentration; therefore, oral clonidine usually needs to be continued on Day 2. Therefore, oral clonidine may be administered on day 2 as clinically indicated, depending on vital signs and opiate withdrawal symptoms. The clonidine dose may be increased to either 0.2 mg q

6 hrs or 0.1 mg q 3 hrs (but not to exceed 0.8 mg qd) as long as the vital signs sitting and standing are normal. Apply caution, observation and same withholding rules as in Day 1.

Days 3-6

The patch(es) given on Day 1 will provide sustained blood levels of clonidine for up to 7 days. However, if the patient does not tolerate the patches (i.e., they have a rash or persistent hypotension), the patch(es) should be discontinued and oral clonidine administered in its place in doses similar to that given on Day 2, but with adjustments as clinically indicated, through Day 7. Vital signs (sitting and standing) will be checked on every scheduled clinic visit or as instructed by the treating physician.

Day 7

On Day 7, remove all clonidine patches. Evaluate the patient's tolerance of clonidine, vital signs sitting and standing, opiate use during the detoxification, and symptoms of opiate withdrawal to decide whether or not to replace the patches or continue with oral clonidine. A common course is to reduce the dose by one-half for the second week.

Days 8-13

Continue to monitor vital signs for any changes of B.P. and pulse. Discontinue clonidine administration and remove any remaining patches by Day 13.

Day 14

Monitor vital signs for any rebound elevation of B.P.

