14.0 ANALYTICAL PLAN

14.1 Statistical Hypotheses

Primary Efficacy Endpoint: It is hypothesized that BUP/NX detoxification, compared to clonidine, will be associated with a better treatment response. A treatment responder is defined as anyone who completes the 13-day detoxification and whose last urine specimen is negative for opiates. By combining treatment retention with opiate abstinence, a composite number is derived that is indicative of both the patients' tolerance to the treatment and the desired outcome of abstinence at the completion of a short-term detoxification procedure. Note that there is no issue concerning the handling of missing data when utilizing this definition of "responder." Patients who fail to either come in or provide a urine sample are, by definition, non-responders.

Other Primary Efficacy Endpoint: Other primary efficacy endpoints were selected to examine the effect of treatment on 1) opiate and other drugs of abuse abstinence throughout the detoxification period and during longer term follow-up, 2) withdrawal symptoms, 3) treatment retention, 4) safety, 5) patient satisfaction with the treatment and 6) extent of ancillary medications dispensed to provide a comprehensive overview of the clinical efficacy and safety of the two treatment regimens.

Hypotheses for the other primary outcome measures include that BUP/NX detoxification, compared to clonidine, will:

- 1. Increase the number and consecutive duration of opiate and all drug-free urine specimens during detoxification and follow-up.
- 2. Increase the number of days retained in treatment.
- 3. Decrease the amount of ancillary medications needed to treat withdrawal symptoms.
- 4. Lessen the severity of withdrawal symptoms as assessed by COWS, ARSW, and VAS.
- 5. Lessen the severity of dependence or abuse as assessed by ASI Lite.

6. Improve the quality of life as assessed by the SF-36 questionnaire and satisfaction with treatment (CSQ).

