14.2.2 Other Primary Outcomes

Other Primary outcomes include:

- 1. The number of urine specimens negative for opiates per patient (a maximum of 4 per patient).
- 2. The number of consecutive urine specimens negative for opiates per patient (maximum of 4).
- 3. The number of urine specimens negative for all drugs (opiates, methadone, cocaine, amphetamines, benzodiazepines, and cannabinoids) per patient (a maximum of 4 per patient).
- 4. The number of days retained in treatment (total days in treatment is the number of days since the start of treatment and the last day of treatment).
- 5. The frequency of dispensing of ancillary medications, by indication (anxiety or restlessness, bone pain or arthralgias, nausea, diarrhea, or insomnia).
- 6. The probability of remaining in treatment and being opiate-free at each urine collection.
- 7. The probability of remaining in treatment and being totally drug-free (negative urine tests for opiates, methadone, cocaine, amphetamines, benzodiazepines, and cannabinoids) at each drug collection.
- 8. The number and severity of adverse events.
- 9. The COWS score during treatment and 1-month follow-up.
- 10. The ARSW score during treatment and 1-month follow-up.
- 11. The VAS score during treatment.
- 12. The ASI Lite score during follow-up.
- 13. The CSQ score at the final visit.
- 14. The SF-36 score during follow-up.

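### Retention has two incompatible definitions, and the one that counts medication days can understate it in the clonidine arm only

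*Protocol*

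**What the plan says.** **Retention.** The synopsis (3.0, outcome assessments) states: "Treatment retention will be calculated as the number of days each patient received his/her detoxification medication". Section 14.2.2, item 4, lists days retained among the other primary outcomes and explains it differently: "total days in treatment is the number of days since the start of treatment and the last day of treatment". Neither place says whether treatment means the drug or the programme.

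**Primary endpoint.** In section 14.1 a responder is "anyone who completes the 13-day detoxification and whose last urine specimen is negative for opiates". The same paragraph describes the composite in these terms: "By combining treatment retention with opiate abstinence, a composite number is derived". It adds that patients who do not come in, or who give no sample, are non-responders. Section 5.0 is narrower on the urine: "whose last urine specimen collected on day 13 or 14 is negative for opiates". Section 14.3 builds the evaluable population on completing the same 13-day procedure. Completion is not defined in any of these places.

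**Regimens.** Section 11.5.1 schedules a BUP/NX dose for every day from 1 to 13. Section 11.5.2 has all clonidine patches removed on Day 7 and the patient evaluated "to decide whether or not to replace the patches or continue with oral clonidine". It describes halving the dose for the second week as common, and it ends clonidine by Day 13. On Day 1, if systolic pressure is below 100 mm Hg or heart rate is below 56 bpm, the clonidine test dose is withheld and the instruction is: "Reassess patient if clinically warranted or discontinue the patient from the study".

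**The concern.** Retention is a named efficacy outcome and is to be tested between arms (14.4). Two definitions that can disagree leave the analyst a choice after the data are in. One of them also works unequally. A count of medication days is fixed by schedule at 13 for an adherent BUP/NX patient. For an adherent clonidine patient it depends on when the clinician chose to stop the drug. A patient who no longer needs clonidine but keeps attending would look like an early dropout.

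The same undefined notion sits inside the primary endpoint and the evaluable population. The trial is open-label, so staff who know the arm would judge completion. Two smaller looseness problems sit nearby: the urine that decides response, and a post-randomisation check that can remove patients from one arm only.

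**Working it through.** The plan gives no figure for retention or for early stopping of clonidine, so there is none to reproduce on this point. The only related figure is the sample size in 14.6: 240 and 120 patients, 30% versus 20% responders, 90% power. The normal approximation in step 3 gives 52.6% two-sided power for those inputs. That is a separate matter; only the group sizes and the 20% rate are used below.

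**1. The two definitions applied to the same patients.** Assumption: a day wearing a patch counts as a day medication was received, which the protocol does not say. Elapsed time is shown as 12 or 13 (6 or 7) because 14.2.2 does not say whether the first day is counted.

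| Patient | Synopsis | 14.2.2, treatment = drug | 14.2.2, treatment = programme |
|---|---|---|---|
| BUP/NX, every dose, attends to Day 13 | 13 | 12 or 13 | 12 or 13 |
| Either arm, one whole day without drug mid-course, attends to Day 13 | 12 | 12 or 13 | 12 or 13 |
| Clonidine not continued after Day 7, attends to Day 13 | 7 | 6 or 7 | 12 or 13 |
| Clonidine not continued after Day 7, leaves on Day 7 | 7 | 6 or 7 | 6 or 7 |

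The last two patients differ in what retention is meant to measure, yet the synopsis rule scores them alike. Section 14.2.2 separates them only if treatment means the programme.

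**2. Effect on mean retention under the synopsis rule.** If a share f of the clonidine arm stops at Day 7 and attends to Day 13, the arm mean falls by (13 − 7) × f = 6f days. The protocol gives no f. At f = 10% the fall is 0.6 days; at f = 30% it is 1.8 days.

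**3. Effect on the primary endpoint, only if completion is read as medication to Day 13.** Let true response be p = 0.20 in both arms, and let a share m of clonidine responders be scored as non-completers. The scored clonidine rate is 0.20(1 − m) and the scored difference is d = 0.20m. With n = 120 and 240, pooled rate q, and

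s0 = √[q(1 − q)(1/120 + 1/240)], s1 = √[pc(1 − pc)/120 + 0.20 × 0.80/240],

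the chance of p<0.05 is Φ((d − 1.96 s0)/s1) + Φ((−d − 1.96 s0)/s1).

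- m = 10%: pc = 0.18, q = (21.6 + 48)/360 = 0.1933, s0 = 0.0442, s1 = 0.0436. Chance = 0.063 + 0.007 = 7.0%.
- m = 25%: pc = 0.15, q = (18 + 48)/360 = 0.1833, s0 = 0.0433, s1 = 0.0416. Chance = 0.201 + 0.001 = 20.2%.

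The nominal rate is 5%, and the excess falls on the side of BUP/NX. The values of m are assumptions without a source in the protocol.

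**4. The deciding urine.** Take a patient who attends throughout, has a negative day 10/11 sample and gives none on day 13 or 14. Under 5.0 this is a non-responder. Under the responder sentence in 14.1, taken alone, it is a responder. Under the missing-sample sentence in 14.1 it is a non-responder again.

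**5. The Day-1 check.** Sections 8.0 and 11.4 place randomisation after eligibility is established; the check in 11.5.2 belongs to the clonidine procedure and so comes after assignment. Section 14.2.1 uses all randomised patients as denominator, so a patient discontinued there counts as a clonidine non-responder. Inclusion criterion 2 (9.1) already applies the same pressure and pulse limits to both arms. Only patients whose readings change after screening are therefore exposed, together with any caught by the PR-interval check, and reassessment is offered as an alternative.

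**The case against.** A reader might infer that correctly treated clonidine patients will be scored as non-responders, so that the primary comparison is biased as written. The protocol does not support that. It never equates completion with 13 medication days, and mentioning retention when describing the composite is not a rule. The one operational rule in 14.1 concerns coming in and giving urine, and 11.5.2 keeps clonidine patients under monitoring through Day 14. On an attendance reading, early stopping leaves the primary endpoint untouched.

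Other objections also stand in part:

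- Vital-sign rules skip single oral doses within a day. A skipped dose is not a lost medication day, so this is weak evidence of undercounting.
- The course that 11.5.2 calls common after Day 7 is continuation at a reduced dose. Stopping is permitted, but its frequency is not given.
- Section 14.1 says the composite should reflect tolerance of treatment. A clonidine patient who leaves because of intolerance is an intended failure, not a misclassified one.
- If treatment in 14.2.2 means the drug, early stopping shortens both measures. Choosing 14.2.2 over the synopsis would then not cure the imbalance.
- The missing-sample sentence shows that the day 13/14 urine is probably what 14.1 intends.
- The Day-1 check repeats thresholds already applied at entry. A reader might suppose that it removes a sizeable part of the clonidine arm; nothing in the protocol supports such a number.

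None of this reconciles the two retention definitions, or makes the synopsis count work equally in both arms.

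**Conclusion.** The point holds for retention. The synopsis and 14.2.2 define it incompatibly, and the synopsis count can understate it in the clonidine arm for patients who are still attending: about 7 days instead of 13 for one stopped at Day 7. The shift in the arm mean is 6 days times the share so stopped, and that share is unknown.

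For the primary endpoint the bias is conditional. It arises only if completion is read as medication to Day 13, a reading the text leaves open. The 7% and 20% figures illustrate that case; they do not estimate this trial's error rate. The difference in urine wording is real, but the protocol's own missing-sample rule largely contains it. The Day-1 check is a one-arm route out after randomisation that probably touches few patients. These points should be fixed because the definitions conflict and the ambiguity works against one arm, but they do not show the primary analysis to be invalid.

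**What to change.** Use one arm-neutral set of definitions in the synopsis and in 5.0, 14.1, 14.2.2 and 14.3:

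- **Retention:** days from first dose (counted as day 1) to the last attended study day, inpatient or clinic, capped at 13.
- **Completion:** attending the day 13 or 14 visit, whether or not study drug was given that day. Allowing either day covers most clinic closures. Patients who leave because of intolerance remain non-completers.
- **Urine:** the day 13 or 14 specimen, named in every statement of the responder definition. A final-visit sample from an early terminator does not stand in for it.

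Finish the Day-1 vital-sign and ECG check, with whatever thresholds the sponsor keeps, before the randomisation envelope is opened. This concerns the order of steps; it changes no clinical rule and does not displace any safety check the sponsor wants before dosing.

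The cost is protocol wording and a change of sequence. Attendance can be taken from the dated daily assessments in Table 1; the dosage log in 12.19 records drug amounts and would not serve. The downside is that patients who attend but miss doses count as retained in either arm, including any taken off clonidine for intolerance who keep attending. Days on medication can still be reported separately as exposure.

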4.0 BACKGROUND AND RATIONALE

For decades clinicians have been frustrated by the inability to adequately detoxify opiate addicts because opiate-based detoxification, one of the most effective means to achieving that goal, has been unavailable outside the very restrictive confines of narcotic treatment programs (NTPs). This frustration has been more acutely felt over the past several years because of the rise in heroin use and the recent interest in ultra-rapid opiate detoxification (UROD), which unfortunately has often been more a matter of commerce than medicine. Buprenorphine (Subutex), and BUP/NX (Suboxone) in particular, may change all of that.

Buprenorphine is a high affinity, partial μ-opioid agonist pending FDA approval as a pharmacotherapy for opioid dependence (Bickel and [name], 1995; [name] *et al.*, 1994). Treatment with buprenorphine in the United States will employ a sublingual combination tablet containing buprenorphine and naloxone in a 4:1 ratio (Chiang and Hawks, 1994; Chiang *et al.*, 1996a, 1996b, Fudala *et al.*, 1998). This combination tablet was developed to help mitigate potential diversion and abuse of buprenorphine once it becomes available for widespread clinical use. Bioavailability studies with sublingual solution and tablet formulations of buprenorphine indicate tablet preparations of buprenorphine may be about 60-70% of the corresponding sublingual solution dose (Nath et al., 1999; Schuh and Johanson., 1999; [name] *et al.*, unpublished). Thus, combination tablet dosages used in clinical practice may need to exceed those shown to be effective in prior controlled studies with the sublingual solution.

Clinical research in the last 10 years has established that buprenorphine (and BUP/NX) is a safe and effective alternative to methadone (Bickel et al., 1988a; Johnson et al., 1992; Strain et al., 1994; [name] et al., 1996, 1998; Uehlinger et al., 1988; [name] et al., in press 2000a) and levomethadyl acetate hydrochloride (LAAM; Chutuape et al., 1999) that produces significant and substantial improvements over time in psychosocial functioning (Strain et al., 1996). Buprenorphine also has unique features that permit novel uses, which may alter current strategies for maintenance and detoxification (Bickel and [name], 1995; [name] et al., 2000, in press 2000b). In particular, buprenorphine's ceiling on agonist activity decreases the danger of overdose, may limit its abuse liability (Walsh et al., 1994, 1995) and confers low toxicity even at high intravenous doses (Lange et al., 1990; Huestis et al., 1999), increasing the dose range over which it may be safely administered. Buprenorphine can also produce sufficient tolerance to block the effects of exogenously administered opioids (Bickel et al., 1988b; Rosen et al., 1994; Walsh et al., 1995), suggesting that it may help reduce illicit opioid use. Finally, buprenorphine's slow dissociation from μ -opioid receptors (Rance and Dickens, 1978) not only results in a long duration of action but also diminishes withdrawal signs and symptoms upon its discontinuation ([name] et al., 1994; Bickel et al., 1997; Cheskin et al., 1994; Fudala et al., 1990; Jasinski et al., 1978; Seow et al., 1986), making it particularly useful for opioid detoxification. Such qualities may impact positively on detoxification outcomes by

permitting accelerated buprenorphine detoxifications to be used without inducing significant withdrawal distress.

In designing a buprenorphine detoxification program, three main objectives should be met. First, patient compliance and treatment retention should be maintained. Second, opioid abstinence should be achieved. Third, minimal abstinence symptomology should result from the dose reduction schedule in order to minimize the risk for relapse. The purpose of this study is to determine the clinical utility of BUP/NX as compared to clonidine (an alpha-2 adrenergic agonist) for short-term opiate detoxification with treatment initiated in inpatient settings. Clonidine hydrochloride has been previously shown to be a safe and effective medication for detoxifying individuals from narcotics (Gold et al., 1980). Advantages of clonidine include its non-narcotic status and accessibility to primary care providers in both inpatient and outpatient settings. However, side effects such as postural hypotension and sedation (Charney et al., 1981; Gossop, 1988) or unrelieved withdrawal symptoms such as insomnia can lead to early patient attrition and be particularly difficult to manage on an outpatient basis. Although in controlled clinical trials buprenorphine appeared to be more effective than clonidine for alleviating withdrawal symptoms (Nigam et al., 1993; O'Connor et al., 1997), more research is needed comparing the relative effectiveness of these two medications in community treatment settings. In particular, studies are needed in community-based clinics that use the product formulation of buprenorphine (i.e., the BUP/NX tablet) anticipated to be marketed.

How BUP/NX can best be used in a variety of clinical settings to benefit those patients who are not served by the current treatment system remains to be investigated. There are ongoing efforts under NIDA's auspices to introduce buprenorphine for treatment of opiate dependence in physician office-based practice. These protocols are expected to engage patients in treatment for up to a year. Little data have been generated, however, for the shorter-term use of buprenorphine and BUP/NX for detoxification from opiates, a strategy that mirrors much of the opiate detoxification as currently practiced outside of the NTPs. The diversity of clinics in the CTN provides an unparalleled opportunity to conduct such a clinical endeavor. The CTN will benefit directly from the fruits of research while at the same time contribute to a gap in the data on buprenorphine both for labeling purposes and post-marketing surveillance. The CTN leadership had voted as its top priority with highest clinical relevance, BUP/NX for opiate detoxification. This is a "win/win" vote for NIDA and the CTN.

